7.3 REPORTING OF SERIOUS ADVERSE EVENTS

Any AE that meets protocol-defined serious criteria or meets the definition of Adverse Event of Special Interest that require expedited reporting must be submitted immediately (within 24 hours of awareness) to OSRO Safety using the CCR SAE report form. Any exceptions to the expedited reporting requirements are found in section [7.4](#).

All SAE reporting must include the elements described in section [7.2](#).

SAE reports will be submitted to the Center for Cancer Research (CCR) at:

[contact] and to the CCR PI and study coordinator. CCR SAE report form and instructions can be found at:

<https://ccrod.cancer.gov/confluence/display/CCRCRO/Forms+and+Instructions>

Following the assessment of the SAE by OSRO, other supporting documentation of the event may be requested by the OSRO Safety and should be provided as soon as possible.

7.4 WAIVER OF EXPEDITED REPORTING TO CCR

As death due to disease progression is part of the study objectives, and captured as an endpoint in this study, it will not be reported in expedited manner to the sponsor. However, if there is evidence suggesting a causal relationship between the study drug and the event, report the event in an expedited manner according to section [7.3](#).

7.5 SAFETY REPORTING CRITERIA TO THE PHARMACEUTICAL COLLABORATORS

7.5.1 Reporting to Astellas

All events listed below must be reported in the defined timelines to [contact].

Short Title: Enzalutamide Vaccine in mCRPC

Version Date: 03/29/2022

The CCR Office of Regulatory Affairs will send all reports to the manufacturer as described below.

The Investigator should complete and submit an SAE Medwatch 3500 Form, containing all information that is required by the Regulatory Authorities, to Astellas by either e-mail or fax within 24 hours of awareness whether or not related to the study drug. If submission of this SAE by email or fax or is not possible within 24 hours, the local drug safety contact (IRB, Investigator, etc.) should be informed by phone.

The SAE documentation, including the Medwatch 3500 Form and available source records, should be emailed or faxed to:

Astellas Pharma Global Development – United States
Email: [contact]
[contact]

The following minimum information is required:

- Study number/IIT regulatory identifier
- Subject number, sex and age
- The date of report
- A description of the SAE (event, seriousness of the event)
- Causal relationship to the study drug

Follow-up information for the event should be sent within 7 days as necessary.

7.6 REPORTING PREGNANCY

All required pregnancy reports/follow-up to OSRO will be submitted to:

[contact] and to the CCR PI and study coordinator. Forms and instructions can be found here:

<https://ccrod.cancer.gov/confluence/display/CCRCRO/Forms+and+Instructions>

7.6.1 Paternal Exposure

Male patients should refrain from fathering a child or donating sperm during the study and for three (3) months after the last dose of enzalutamide.

Pregnancy of the patient's partner is not considered to be an AE. However, the outcome of all pregnancies (spontaneous miscarriage, elective termination, ectopic pregnancy, normal birth, or congenital abnormality) occurring from the date of the first dose until three (3) months after the last dose should, if possible, be followed up and documented.

7.7 REGULATORY REPORTING FOR STUDIES CONDUCTED UNDER CCR SPONSORED IND

Following notification from the investigator, CCR, the IND sponsor, will report any suspected adverse reaction that is both serious and unexpected. CCR will report an AE as a suspected adverse reaction only if there is evidence to suggest a causal relationship between the study product and the adverse event. CCR will notify FDA and all participating investigators (i.e., all investigators to whom the sponsor is providing drug under its INDs or under any investigator's IND) in an IND safety report of potential serious risks from clinical trials or any other source, as soon as possible, in accordance to 21 CFR Part 312.32.

All serious events will be reported to the FDA at least annually in a summary format.

7.8 SPONSOR PROTOCOL DEVIATION REPORTING

A Protocol Deviation is defined as any non-compliance with the clinical trial Protocol, Manual of Operational Procedures (MOP) and other Sponsor approved study related documents, GCP, or protocol-specific procedural requirements on the part of the participant, the Investigator, or the study site staff inclusive of site personnel performing procedures or providing services in support of the clinical trial.

It is the responsibility of the study Staff to document any protocol deviation identified by the Staff or the site Monitor in the CCR Protocol Deviation Tracking System (PDTs) online application. The entries into the PDTs online application should be timely, complete, and maintained per CCR PDTs user requirements.

In addition, any deviation to the protocol should be documented in the participant's source records and reported to the reviewing IRB per their guidelines. OSRO required protocol deviation reporting is consistent with E6(R2) GCP: Integrated Addendum to ICH E6(R1): 4.5 Compliance with Protocol; 5.18.3 (a), and 5.20 Noncompliance; and ICH E3 16.2.2 Protocol deviations.

8 CLINICAL MONITORING

Clinical site monitoring is conducted to ensure:

- that the rights of the participants are protected;
- that the study is implemented per the approved protocol, Good Clinical Practice and standard operating procedures; and
- the quality and integrity of study data and data collection methods are maintained.

Monitoring for this study will be performed by NCI CCR Office of Sponsor and Regulatory Oversight (OSRO) and Regulatory Oversight Support (SROS) Services contractor. Clinical site monitoring activities will be based on OSRO standards, FDA Guidance E6(R2) Good Clinical Practice: Integrated Addendum to ICH E6(R1) March 2018, and applicable regulatory requirements.

Details of clinical site monitoring will be documented in a Clinical Monitoring Plan (CMP) developed by OSRO. CMPs will be protocol-specific, risk-based and tailored to address human subject protections and integrity of the study data. OSRO will determine the intensity and frequency of monitoring based on several factors, including study type, phase, risk, complexity, expected enrollment rate, and any unique attributes of the study and the site. The Sponsor will conduct a periodic review of the CMP to confirm the plan's continued appropriateness. A change

to the protocol, significant or pervasive non-compliance with GCP, or the protocol may trigger CMP updates.

OSRO SROS Monitoring visits and related activities will be conducted throughout the life cycle of each protocol. The first activity is before the study starts to conduct a Site Assessment Visit (SAV) (as warranted), followed by a Site Initiation Visit (SIV), Interim Monitoring Visit(s) (IMVs), and a study Close-Out Visit (COV).

Some monitoring activities may be performed remotely, while others will occur at the study site(s). Monitoring visit reports will describe visit activities, observations, and associated action items or follow-up required for resolution of any issues, discrepancies, or deviations. Monitoring reports will be distributed to the study PI, NCI CCR QA, CCR Protocol Support Office, coordinating center (if applicable), and the Sponsor regulatory file.

The site Monitor will inform the study team of any deviations observed during monitoring visits. If unresolved, the Monitor will request that the site Staff enter the deviations in the CCR Protocol Deviation Tracking System (PDTs) for deviation reporting to the Sponsor and as applicable per institutional and IRB guidance.

9 STATISTICAL CONSIDERATIONS

The primary objective is to determine if PSA-TRICOM combined with enzalutamide will increase time to progression in chemotherapy-naïve metastatic castration resistant prostate cancer patients compared to enzalutamide alone.

Secondary objectives include determining if PSA-TRICOM combined with enzalutamide will increase overall survival and/ or delay PSA progression compared to enzalutamide alone, and. Tumor growth rates at various time points will also be determined and compared as a secondary objective.

Exploratory objectives include comparing the immune response in patients between the two arms. Immune response evaluation will include CD4 cells, CD 8 cells, PSA-specific T-cells, natural killer cells, Regulatory T-cells, Regulatory T-cell function, cytokines, naïve thymic emigrants. The study will also aim to determine the association between immunologic parameters and clinical outcomes

The study is based on an assumption of a median time to progression of 10 months in chemotherapy-naïve mCRPC patients. Should the PREVAIL trial results be reported prior to the opening of this trial, and if they are substantially different from this estimate, adjustments in this plan will be made accordingly. The primary endpoint will be the comparison of the Kaplan-Meier curves for the two arms using a stratified log-rank test. The trial will be conducted using a phase 2.5 design (one tailed 0.10 alpha level test) [41].

If we assume that the arms will have time to progression medians of 10 vs. 18 cycles (which would have hazards of 0.0693 and 0.0385, respectively, and a hazard ratio of 1.80), and if patients are accrued for 36 months and the last one enrolled is followed for up to 12 more months (48 months total follow-up from time of enrolling first patient), and a total of 52 events are observed, then 36 patients per arm provides 80% power to compare the two arms.

Patients will be stratified based on previous immunotherapy used as cancer treatment.

Survival will be compared between the two arms, as a secondary endpoint, using Kaplan-Meier curves and a stratified log-rank test. Continuous parameters will be compared between the two arms using appropriate non-parametric tests, such as a Wilcoxon rank sum test. Immune outcomes and clinical outcomes will be compared using appropriate measures, such as Spearman correlation, Fisher's exact test, or Wilcoxon rank sum test. All secondary outcomes will be reported without formal adjustment for multiple comparisons but in the context of the number of such tests performed.

In order to allow for a small number of inevaluable patients, up to 76 total patients may be enrolled in order to yield 72 total evaluable patients. If the study is able to accrue approximately 2 patients per month, then accrual can be completed in approximately 3 years.

This projected accrual time frame is based on a previous trial in mCRPC which recently enrolled at the NCI. Trial 11-C-0195 enrolled 52 patients in under 2 years, therefore it would be feasible to accrue the number of patients required in this design.

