2.3.1 Treatment Assignment and Randomization/Stratification Procedures

Cohorts

Number	Name	Description
1	Prostate Cancer Patients	Patients with chemotherapy naïve metastatic castrate-resistant prostate cancer

Short Title: Enzalutamide Vaccine in mCRPC

Version Date: 03/29/2022

Arms

Number	Name	Description
1	A	Enzalutamide alone
2	B	Enzalutamide with PSA-TRICOM

Stratifications

Name	Distinct Options	Notes
Prior Immunotherapy	Yes No	

Randomization and Arm Assignment

Patients must be registered with Central Registration Information Services within 24 hours after signing the consent. All Patients on study will be directly assigned to cohort 1.

Patients in cohort 1 will be randomized within 24 hours after registration. Block randomization will be used to randomly assign patients in a 1:1 manner between arms A and B. Randomization will be stratified by prior immunotherapy used as cancer treatment.

For randomization, authorized staff should call [contact] between the hours of 8:30 a.m. and 5:00 p.m., Monday through Friday. A recorder is available during non-working hours.

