4 BIOSPECIMEN COLLECTION

4.1 CORRELATIVE STUDIES FOR RESEARCH

4.1.1 Parameters of Immune Response

(Refer to [4.1.2](#) Immunologic Assays for detail):

- IFN-gamma ELISPOT assay for PSA-specific T lymphocytes
- CD4 T Cell Proliferation
- Antibodies to PSA and other tumor antigens
- Leukocyte CD3, CD4, CD8 subsets; CD4:CD8 ratio will be drawn at baseline and each cycle while the patient remains on trial.
- Immunologic profiles will be investigated to evaluate whether enhanced thymopoiesis might be present during vaccine administration; these immunologic profiles are to include enumeration of recent thymic emigrants by quantification of T-cell subsets by multiparameter flow cytometry.

- The results of the HIV antibody test need to be available before treatment to determine eligibility.
- HLA class I expression (HLA typing) with A2 subtyping (obtain any time prior to first vaccine).
- Immunologic studies will be repeated more frequently if clinically indicated. Any abnormalities potentially related to treatment will be followed until they have resolved or have been determined not to be treatment-related.

4.1.1.1 All patients who are HLA A02 or A03 (approximately 50% of the US population) will undergo leukapheresis every 12 weeks while on-study when available and with the consent of the patient. Patients may refuse.

- IFN-gamma ELISPOT assay
- T cell proliferation
- Antibody Response
- Flow cytometry analysis of thymic emigrants
- Natural Killer (NK) Cells
- Regulatory T Cells
- Additional Assays: Blood samples may be used for additional research studies, which may include phenotypic and functional analysis of immune-cell subsets and analyses for cytokines, chemokines, antibodies, tumor associated antigens, anti-glycan antibodies and/or other markers.

Details on these tests can be found in [4.1.2](#).

4.1.1.2 **Collection of blood samples for immune assays:** Blood samples may be obtained at baseline, 1 month, 3 months, 12 months, 18 months, then every 6 months at restaging while on study. All patients will have 6 (10ml) green top tubes and 2 (8ml) SST drawn prior to treatment at designated timepoints.

4.1.1.3 The samples will be processed at:

Clinical Services Program
 NCI Frederick Cancer Research and Development Center
 [name]
 [name]
 [contact]

On days samples are drawn, [name] at CSP should be notified (phone: [name]; fax [name]). She will arrange courier delivery of the specimens to the processing lab.

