4.1.2 Immunological Assays

4.1.2.1 IFN-gamma ELISPOT

We plan to examine the immune response in selected patients (HLA-A2-positive).

HLA class I expression (HLA typing) with A2 subtyping will be done prior to enrollment. Results will not be required prior to enrollment.

Lymphocytes will be separated from heparinized blood using density gradient centrifugation. The lymphocytes will then be placed in human AB serum with 10% DMSO and stored in liquid nitrogen. When samples are available from pre- and post-treatment, the ELISPOT assay will be performed. The ELISPOT assay, measuring IFN-gamma production, is used to determine CTL precursor frequency to peptides from PSA, PSMA, MUC-1, PSCA, CEA, and PAP in both pre- and post-vaccination peripheral blood mononuclear cells, as previously described [37, 38]. Briefly, 96-well mL HA plates (Millipore Corporation, Bedford, MA) are coated with 100 μ l/well of capture MAb against human IFN-gamma at a concentration of 10 μ g/mL for 12h at RT. Plates are blocked for 30 min with RPMI 1640 plus 10% human Ab serum 2×10^5 PBMC are added to each well. PSA-3A pulsed C1R-A2 cells are added into each well as antigen-presenting cells (APC) at an effector:APC ratio of 1:1. Unpulsed C1R-A2 cells are used as a negative control. HLA-A2 binding flu matrix peptide 59-66 is used as a positive peptide control [39]. We also perform each sample with 6 replicates to control for variability. In addition, each sample is run with a flu peptide control (pre- and post-vaccine) as well as samples from a “normal” control HLA-A2-positive individual with previously determined levels of flu-specific T-cell precursors. Cells are incubated for 24 h and lysed with phosphate-buffered saline (PBS)-Tween (.05%). Biotinylated anti IFN-gamma antibody diluted to 2 μ g/mL in PBS-Tween containing 1% bovine serum albumin (BSA) is added and incubated overnight in 5% CO₂ at 37°C. Plates are washed 3 times and developed with avidin alkaline phosphatase (GIBCO/BRL, Grand Island, NY) for 45 min. After washing the plates 3 times, each well is examined for positive dots. This assay will be performed in the Genitourinary Malignancies Branch, NCI, NIH. The number of dots in each well will be counted by 2 separate investigators in a *blinded manner*, and the frequency of responding cells will be determined.

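### Section 9 does not say that the immune comparison will use the baseline value or the randomization stratum; a baseline-adjusted rank analysis would do as well or better at no cost

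*Combined protocol and SAP*

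**What the plan says.** Section 9 makes the immune comparison a between-arm one: "Exploratory objectives include comparing the immune response in patients between the two arms". The only rule there for comparing continuous quantities between arms is "Continuous parameters will be compared between the two arms using appropriate non-parametric tests, such as a Wilcoxon rank sum test". It gives no time point, no baseline term and no stratum, and it does not say what is ranked. The sentence covers continuous parameters in general, so it also appears to govern tumor growth rates, which Section 9 lists as a secondary objective.

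Baseline data are planned. For T-cell subsets, Section 4.1.1 says that the "CD4:CD8 ratio will be drawn at baseline and each cycle while the patient remains on trial". For the other assays, Section 4.1.1.2 says "Blood samples may be obtained at baseline, 1 month, 3 months, 12 months, 18 months, then every 6 months at restaging while on study". Section 4.1.2.1 makes ELISPOT a paired assay: "When samples are available from pre- and post-treatment, the ELISPOT assay will be performed".

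On strata, Section 2.3.1 says "Randomization will be stratified by prior immunotherapy used as cancer treatment". Section 9 carries this factor into the log-rank tests for TTP and survival, but mentions none for continuous parameters.

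**The concern.** A two-sample rank-sum test on follow-up values leaves out a covariate that should already be in hand. When baseline and follow-up are correlated, this costs power and leaves chance baseline imbalance in the comparison. Ranking the change from baseline uses the baseline, but inefficiently when the correlation is low.

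The plan does not choose between these two, so the choice could be made after the data are seen, across many immune parameters and several visits.

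The sample is small: 36 evaluable men per arm at full accrual, and fewer for ELISPOT, which Section 4.1.2.1 limits to HLA-A2-positive men. Section 6.5.2 records that accrual closed in December 2016, so the method of analysis is the main remaining way to gain precision. Section 1.2.6 expects the immune data to guide how vaccine is combined with enzalutamide in later trials.

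**Working it through.** **The plan's own figure.** The only power statement concerns TTP: 52 events, hazard ratio 1.80, one-sided alpha 0.10, 80% power. Schoenfeld's formula gives Φ(√(52/4) × ln 1.80 − 1.282) = Φ(2.119 − 1.282) = 0.799, so the figure reproduces. No power, effect size or alpha is stated for any immune comparison.

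**Inputs.** From the documents: 36 per arm, 1:1 allocation, a Wilcoxon-type test, and a scheduled baseline. Assumed: two-sided 0.05, normal values, rho of 0.3, 0.5 or 0.7, and an effect giving the follow-up Wilcoxon 80% power.

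**Formula.** The Wilcoxon efficiency under normality is 3/π, so the effective n per arm is 36 × 3/π = 34.4. With d the between-arm difference in SD units, power = Φ( d / √(f × 2/34.4) − 1.960 ). The variance factor f is:
- follow-up value: 1
- change from baseline: 2(1 − rho)
- baseline-adjusted: 1 − rho²

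The reference effect is d = (1.960 + 0.842) × √(2/34.4) = 0.676 SD. For example, at rho 0.5 the adjusted analysis has f = 0.75, and power = Φ(2.802/0.866 − 1.960) = Φ(1.275) = 0.899.

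**Results.** Power in %, by formula, with simulation in brackets (3,000 runs per row, Quade's rank ANCOVA):

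| rho | Wilcoxon, follow-up | Wilcoxon, change | Rank ANCOVA | Gain over the better Wilcoxon |
|---|---|---|---|---|
| 0.3 | 80.0 (79.2) | 65.8 (64.7) | 83.6 (82.1) | 3.6 (2.9) |
| 0.5 | 80.0 (79.3) | 80.0 (79.1) | 89.9 (87.7) | 9.9 (8.4) |
| 0.7 | 80.0 (78.3) | 95.1 (94.6) | 97.5 (95.6) | 2.4 (1.0) |

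The formula is somewhat optimistic for the adjusted test, so the conclusion uses the simulated values. Two further simulations with an effect of 0.685 SD gave rank ANCOVA 83%, 87% and 96%, and 83%, 89% and 96%. Type I error was 4.7% to 5.3%.

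**Sample-size terms.** At rho 0.3 and 0.5, adjustment matches 36 men per arm analysed on follow-up values with 36 × 0.91 = 32.8 and 36 × 0.75 = 27.0. At rho 0.7 the better Wilcoxon is the one on change. The variance ratio is then 0.51/0.60 = 0.85, or 36 × 0.85 = 30.6 per arm. The 1-point gain at rho 0.7 is small partly because power is already near 95%. At a smaller effect of 0.5 SD, the formula gives the better Wilcoxon 54.5%, 54.5% and 76.3%, against 58.4%, 66.8% and 82.7% adjusted.

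**HLA-restricted subset.** Section 4.1.1.1 puts HLA-A02 or A03 together at about 50% of the US population, so 18 per arm is a rough upper figure for ELISPOT. At 0.5 SD and rho 0.5, power rises from 31.1% to 39.5%. The comparison is underpowered either way.

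**Stratum alone.** Let a share q of men have had prior immunotherapy, and let the strata differ by D SD. The variance explained is R² = q(1−q)D² / (1 + q(1−q)D²), and f = 1 − R². For q from 0.1 to 0.5, the 80% reference becomes 80.2-80.6% at D = 0.25, 80.9-82.3% at D = 0.5 and 83.3-87.9% at D = 1. With no stratum effect and an assumed 10% share, adding strata to rank ANCOVA at rho 0.5 gave 87.3% against 87.8% without them.

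**The case against.** The Wilcoxon test is offered as an example, and the sentence is silent on what is ranked. A reader might infer that the plan ignores the baseline value. The documents do not support this: a Wilcoxon test on change fits the wording and sits naturally with paired ELISPOT samples. That stands, and it limits the point to what the plan does not specify. It does not remove the point, because change does worse than follow-up values at rho 0.3 and gains nothing at rho 0.5.

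A reader might also infer a gain above 5 points for any rho of 0.5 or more. That holds only against follow-up values. Against the better of the two permitted analyses, at the 80% reference, it holds only near rho 0.5.

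The stratum is a weak argument for power. The documents give no stratum sizes and no evidence that prior immunotherapy shifts the immune values.

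Finally, the comparison is exploratory, Section 1.2.6 treats such data as hypothesis-generating, and no decision rule depends on it. Nor is it the only evidence of vaccine effect, since TTP, survival, PSA progression and tumor growth rates are also compared between randomized arms. All of this stands and keeps the point minor.

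**Conclusion.** The point holds as a free improvement to an exploratory analysis. Section 9 does not specify use of the baseline value or the prior-immunotherapy stratum for continuous immune parameters, although both should be available.

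Under the assumed inputs, rank ANCOVA on baseline has about 83%, 88% and 96% power at rho 0.3, 0.5 and 0.7. It matches or beats both readings of the plan, by about 2-3, 8 and 1 points over the better one. An analyst would not need to know rho in advance to choose well. Stratification contributes about 0-2 points when strata differ by 0.25 to 0.5 SD; its main justification is agreement with the randomization.

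The sizes rest on an assumed rho, effect, alpha and normality, none of which the documents give. Nothing here touches the TTP design, whose stated power reproduces, or the primary conclusion.

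**What to change.** Keep the existing sentence, so that tumor growth rates and other continuous parameters still have a named test. Add after it:

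> Continuous immune parameters with a baseline measurement will be compared between arms at each scheduled time by rank analysis of covariance with the baseline value as covariate, stratified by prior immunotherapy where stratum sizes allow; the unadjusted Wilcoxon rank sum test will be a sensitivity analysis.

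This settles what is analysed and when, and it remains non-parametric. The condition on a baseline measurement is needed because Section 4.1.1.2 makes the assay samples permissive; the condition on stratum sizes is needed because those sizes are not stated. The cost is one sentence, with no added patients, samples or visits and with standard software. It should be adopted before the immune data are analysed by arm.

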1.1.3 Exploratory Objectives

- Evaluate the immune response in patients treated with both the combination of PSA-TRICOM and enzalutamide compared to enzalutamide alone. Immune response evaluation will include CD4 cells, CD 8 cells, PSA-specific T-cells, natural killer cells, Regulatory T-cells, Regulatory T-cell function, cytokines, anti-glycan antibodies, naïve thymic emigrants.
- Associate immunologic outcomes with clinical outcomes.

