1.2.6 The Importance of Evaluating the Immunologic Response

Our group at in the GMB and LTIB has previously evaluated immunologic parameters in clinical trials with PSA-TRICOM among several immunotherapy studies. A previous trial in mCRPC patients with PSA-TRICOM alone suggested that patients with greatest magnitude of T-cell-specific response against PSA had favorable clinical outcomes [17]. That same trial also suggested that changes in regulatory T-cell function were also associated with improved clinical outcomes [24]. While these findings are not surrogate markers of response, they have greatly improved our knowledge of a vaccine-generated immune response and provided a better understanding of what factors are potentially important in mounting a sufficient anti-tumor immune response that could be associated with improved clinical outcomes. These and other data have allowed us to optimize vaccines in subsequent clinical trials.

Similarly, immunologic parameters will be valuable in understanding the benefits of PSA-TRICOM with enzalutamide. Are the same associations seen or other changes in natural killer cells or cytokines of greater importance in this combination? Furthermore, baseline immune characteristics will be evaluated to determine if they have the potential to predict responders or likely non-responders to immune combinations. While these hypothesis generating data would have to prospectively evaluated in future clinical trials, it may improve our understanding about how best to deploy vaccines in combination with enzalutamide and other forms of hormonal therapy. If enzalutamide increases naïve T-cell production from the thymus as suggested by the pre-clinical data, this may have important ramifications in the timing of vaccine in future clinical trials. This and other data may also provide information early on in the therapeutic regimen about which patients would benefit from continued vaccine in combination with enzalutamide.

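### Section 9 names only tests that ignore censoring for relating immune to clinical outcomes, which costs power for TTP, OS and PSA progression, and fixes no immune time point or responder definition

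*Combined protocol and SAP*

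**What the plan says.** Section 1.1.3 sets the exploratory aim: "Associate immunologic outcomes with clinical outcomes". It does not say which clinical outcomes. Section 9 gives the method: "Immune outcomes and clinical outcomes will be compared using appropriate measures, such as Spearman correlation", Fisher's exact or Wilcoxon rank sum tests. No Cox model, log-rank test by immune group, landmark or time-dependent analysis is mentioned for this aim, and no immune time point or responder definition is fixed.

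Censored-data methods do appear in Section 9, but for comparing arms. TTP is tested by stratified log-rank, and for OS, "Survival will be compared between the two arms, as a secondary endpoint, using Kaplan-Meier curves and a stratified log-rank test". Immune markers fall under the general rule for arm comparisons: "Continuous parameters will be compared between the two arms using appropriate non-parametric tests, such as a Wilcoxon rank sum test".

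On sampling, Section 4.1.1.2 says: "Blood samples may be obtained at baseline, 1 month, 3 months, 12 months, 18 months, then every 6 months at restaging while on study". The Study Calendar (3.4) agrees: after C4D1, samples come at C13 and C19, then six-monthly. Section 4.1.1.1 adds optional leukapheresis every 12 weeks on study for men who are HLA A02 or A03. Progression ends protocol therapy (3.6.1), and a man is off study after a visit about 30 days later (3.6.2).

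Section 1.2.6 describes the status of the work: "While these hypothesis generating data would have to prospectively evaluated in future clinical trials". It also plans a baseline analysis: "baseline immune characteristics will be evaluated to determine if they have the potential to predict responders or likely non-responders to immune combinations".

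**The concern.** There are two separate problems.

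**Censoring.** The trial's main clinical endpoints (TTP, OS, PSA progression) are times to an event. A rank test on observed times treats a man censored at 14 months because he enrolled late as if he had progressed at 14 months. That blurs a real association. With 36 men per arm there is little power to spare.

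**Guarantee time.** A man gives a 12- or 18-month sample only if he is still on study then. If a responder is anyone with a positive assay at any visit, men who progress late have more chances to qualify, and responders will appear to do better even when the marker is irrelevant.

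Section 1.2.6 hopes these data will improve understanding of how to deploy vaccine with enzalutamide and show early in treatment who benefits from continuing it. A missed or false lead would carry into the next trial.

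**Working it through.** **The plan's own figure.** No power is stated for this aim. The only stated power is for the primary test: 52 events, hazard ratio 1.80, one-sided 0.10. By Schoenfeld, (√52/2) × ln 1.80 − 1.2816 = 2.119 − 1.282 = 0.838, and Φ(0.838) = 79.9%. The stated 80% reproduces, so I take the design inputs as they stand.

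**Amount of censoring.**
- From the stated events: (72 − 52)/72 = 20/72 = 28% for TTP.
- From the design model: 36 months' uniform accrual plus 12 months, exponential times, so the censored fraction is (e^(−12λ) − e^(−48λ))/(36λ). With λ = 0.0693 (arm A) it is (0.435 − 0.036)/2.495 = 16%. With λ = 0.0385 (arm B) it is (0.630 − 0.158)/1.386 = 34%. That is 18 of 72, or 25% overall. I read the time unit as months; Section 9 uses both months and cycles.
- For OS, Section 9 gives no median. Section 1.2.1 cites 35.5 months for enzalutamide in the chemotherapy-naïve phase III trial. With λ = ln 2/35.5 = 0.0195 the fraction is (0.791 − 0.392)/0.703 = 57%.

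**Effect on the named tests.** Simulation with n = 36, censoring uniform on 12 to 48 months, two-sided 0.05, and a normally distributed marker known at the start of treatment.

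| Outcome | Assumed HR per SD | Spearman on observed times | Cox test |
|---|---|---|---|
| TTP, median 18 | 0.6 | 49% | 64% |
| OS, median 35.5 | 0.6 | 31% | 49% |
| TTP, median 18 | 1.8-fold | 59% | 75% |
| TTP, median 10 | 1.8-fold | 71% | 81% |
| OS, median 35.5 | 1.8-fold | 39% | 60% |

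The 1.8-fold rows are a slightly stronger effect (0.6 is 1/0.6 = 1.67-fold). With no association, Spearman rejects 4.8 to 5.7% of the time, so independent censoring weakens real associations and does not create false ones. When both tests are restricted to men progression-free at 12 weeks, TTP power at HR 0.6 is 39% for Spearman against 55% for Cox.

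**Guarantee time.** Simulation of 36 vaccine-arm men with TTP median 18, the blood schedule of Section 4.1.1.2, responses unrelated to TTP, and an assumed chance of a positive assay per sample. Two-sided 0.05 false-positive rates:
- Ever-responder over all on-study samples, Wilcoxon on TTP: 21% to 71% for 5% to 30% positive per sample (62% at 20%).
- Only the 1- and 3-month samples, no landmark: about 7 to 9% for 20 to 30% positive, rising to 18% at 50%.
- Three-month landmark log-rank on the blood schedule: 5 to 8%.
- Baseline markers: no guarantee-time bias, since every man has the value at the start.

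**The case against.** The strongest reply is that the sentence is an open list. It asks for appropriate measures and offers three examples, so a Cox model is not excluded. The clinical outcomes are not named, and several in the protocol suit the named tests: tumor growth rate (Section 9), PSA decline (5.3.1) and objective response (5.3.5). This stands. The plan is silent on a censored-data method for this aim; it does not forbid one.

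A reader might infer that the associations will be spurious, or that the upper false-positive rates above are the plan's error rate. The documents support neither. Censoring alone leaves the size near 5%. The high rates need an ever-responder definition that the plan never states, together with assumed assay positivity.

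Radiographic progression is looked for every 12 weeks (5.3.1), so few men will have it recorded before the 3-month sample. With progression recorded only on 12-week scans, the simulated false-positive rate for the 1- and 3-month samples was 4 to 5%. This also stands, and it is why the bias is called small for early samples. It raises a practical point too: a C4D1 landmark coincides with the first scan, so the plan must say how progression on that scan is classed.

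Some assays will have fewer than 36 men per arm. ELISPOT is planned for HLA-A2-positive patients (4.1.2.1). At an illustrative n = 18 and HR 0.6, TTP power is 26% for Spearman and 35% for Cox. Cox is still better, but neither is adequate.

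Finally, a rank-sum comparison of immune markers between randomized arms is valid, and the wording does not exclude change from baseline. Adjusting for baseline is a matter of efficiency only.

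**Conclusion.** The point holds as a gap in an exploratory analysis. Where the clinical outcome is TTP, OS or PSA progression, the named tests discard information that a Cox model uses. The loss is about 15 percentage points of power on TTP (64 − 49) and 18 on OS (49 − 31), at n = 36, an assumed hazard ratio of 0.6 per SD, and an OS median borrowed from the cited phase III trial. The marker effect is not a document figure; the direction was the same for each effect size and median tried.

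Guarantee-time bias is a conditional risk. It is large if response is pooled over all on-study samples, small if only the 1- and 3-month samples count at moderate positivity, and absent for baseline markers. Because neither a definition nor a time point is fixed, the plan does not exclude the bad case.

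It would go too far to say that Section 1.2.6 makes this analysis the basis for deciding how vaccine is used. It calls the data hypothesis generating and requires prospective evaluation. The primary TTP test, its sample size and the arm comparison of OS are unaffected.

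**What to change.** Amend the association sentence in Section 9 as follows.

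- For TTP, OS and PSA progression, use a Cox model with the immune measure as a continuous covariate, stratified by arm and prior immunotherapy.
- Analyse baseline markers from the start of treatment.
- Analyse the scheduled C4D1 sample by landmark in men still progression-free, stating that progression on the first restaging scan counts as before the landmark.
- Enter later samples only as time-dependent covariates.
- Keep Spearman, Fisher and Wilcoxon for uncensored outcomes such as tumor growth rate, PSA decline and response.
- As an efficiency gain, compare arms on post-treatment immune values adjusted for the baseline value already collected (rank or log-scale ANCOVA).

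The cost is plan wording and a few lines of code, with no new visits, samples or patients. The downside is that men who progress by the landmark leave that one analysis. Under the design medians this is 1 − 0.5^(2.76/10) = 17% of arm A and 1 − 0.5^(2.76/18) = 10% of arm B, taking 12 weeks as 2.76 months. The figure could be lower, because new bone lesions at first restaging may only reset the baseline (5.3.4.2).
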